Combination studies were performed *in vitro* on colon (n=25), pancreas (n=6), and lung (n=15) cell lines. A fixed ratio of GSK1120212 (0.25 μ M) to GSK2141795 (10 μ M) with 3-fold serial dilutions was used in a 3-day proliferation assay. The combination effect was determined by excess over highest single agent (EOHSA), BLISS, and Combination Index (Cl) (<1). Results indicated synergy in 14 colon, 7 lung, and 2 pancreas cell lines; modest synergy in 7 each colon and lung, and 2 pancreas cell lines; additive in 3 colon, 1 lung, and 2 pancreas cell lines; and none in one colon cell line. Synergy was seen in one colon and one lung cell line at concentrations greater and equal to 0.003 μ M (1.9 ng/mL) GSK1120212 and 0.124 μ M (53 ng/mL) GSK2141795. Human steady-state plasma trough concentrations, not correcting for protein binding, similar to the *in vitro* values would be obtained at doses of 0.5 mg (GSK1120212) and 20 mg (GSK2141795). Different values were required for other tumor types.

2.2.4 AKT Inhibitors Dosed in Combination with MEK Inhibitors: Rationale for Treatment of Cervical Cancer

PI3K and RAS-ERK Signaling

Receptor Tyrosine Kinases (RTK) regulate cell growth, proliferation, and differentiation through downstream signals, including the PI3K and the RAS-RAF-MEK-ERK pathways [4] (see figure below).

PI3K enzymes are activated transfer phosphate groups to the inositol ring of phosphatidylinositol to produce the signaling molecule phosphatidylinositol 3,4,5tri-phosphate (PIP3)[5]. Alterations in the PI3K pathway are important in both the development and maintenance of cancer [6]. There are many underlying mechanisms for PI3K pathway activation in cancer, including receptor tyrosine kinase activation or amplification; mutation, deletion, or silencing of negative regulators of the PI3K pathway (such as PTEN) and activation or amplification of downstream kinase mediators [6]. RAS proteins are small GTPases and upon stimulation of an RTK initiates protein kinase cascade through RAF, MEK, and ERK protein kinases [7]. RAS proteins also interact with and signal through PI3K [8]. Specific oncogenic mutations in RAS (K-RAS, N-RAS and H-RAS) as well B-RAF are common some specific solid tumors [9]. Importantly, there is mounting evidence that the PI3K and RAS-ERK pathways have some redundant functions, that there are multiple negative feedback loops between theses pathways and that these interactions may be important for both primary and secondary resistance to inhibitors of either of these pathways in isolation [9].

Rationale for Dual Inhibition of PI3K and RAS- ERK Pathways

Pre-clinical and translational studies support the use of inhibitors of PI3kinase pathway and MEK inhibitors together given the redundancy of the pathways and negative feedback loops. Mouse models of K-RAS driven tumors do not response to either PI3K or MEK inhibition alone, but respond to the combination [10]. Interestingly the different isoforms of RAS (H-RAS, N-RAS) can have differential signaling through PI3K or RAF, suggesting the need for both inhibitors to cease all downstream signaling [8]. PI3K inhibition in patients can result in the activation of several RKTs that can signal through RAS-ERK. In a clinical study of breast cancer, ERK was activated after two weeks of treatment with a rapalog, RAD001 [11]. These data have resulted in the exploration of combination of PI3K and MEK inhibitors in patients. Importantly, Phase I studies of PI3K and MEK inhibitors in combination have shown activity in patients with gynecologic malignancies [12].

PI3K/AKT pathway interacts extensively with the RAF/MEK/ERK pathway. The PI3K/AKT pathway also influences the response of K-RAS mutant cancers to MEK inhibitors, as evidenced by the observation that B-RAF mutant cancers are highly sensitive to MEK inhibition whereas RAS mutant cancers have varied responses. Activating PIK3CA mutations and loss of PTEN function, both of which can lead to activation of AKT signaling, lead to resistance to MEK inhibitors. In tumors with coexisting KRAS and PI3KCA mutations, down-regulation of PI3KCA resensitizes tumors to MEK pathway inhibition. In addition, dual inhibition of the PI3K/AKT and RAF/MEK/ERK pathways also seems to be required for complete inhibition of downstream mTOR effector pathway.

2.3 Rationale for This Study

- Pre-clinical and translational studies support the use of PI3K/AKT and MEK inhibitors together given the redundancy of the pathways and negative feedback loops. Mouse models of K-RAS driven tumors do not response to either PI3K or MEK inhibition alone, but respond to the combination [10]. Interestingly the different isoforms of RAS (H-RAS, N-RAS) can have differential signaling through PI3K or RAF, suggesting the need for both inhibitors to cease all downstream signaling [8]. PI3K pathway inhibition in patients can result in the activation of several RKTs that can signal through RAS-ERK.
- 2. Mutations in both RAS and PI3kinase have been found, with RAS mutations found only in adenocarcinomas and PI3kinase mutations found in both squamous cell and adenocarcinomas.
- 3. Phase I studies of PI3K and MEK inhibitors in combination have shown activity in patients with gynecologic malignancies [12].
- 4. Cervical cancer is the 2nd most common cause of cancer death in the world. Very few options exist for patients with recurrent cervical cancer, and chemotherapy has

little activity in this cancer at the time of recurrence. Newer options are needed for these patients.

2.4 Correlative Studies Background

The successful implementation of personalized medicine with targeted therapies continues to be fraught with unexpected pitfalls, decreasing the speed at which agents can be directed to patients that will benefit. The failure to understand the basic biology of therapeutic targets frequently results in the failure of targeted therapeutics to fulfill their promise. The key road block remains an inability to design and implement biomarker driven trials that match patients to targeted therapies most likely to inhibit their own tumor.

As compared to other women's cancers, there are limited comprehensive data on the rates of RAS-ERK and PI3K pathway alterations in cervical cancer. The translation component of this study is designed in part to help alleviate this knowledge deficit. PIK3CA and PTEN loss have been characterized in one published study at a frequency of approximately 10% [9, 28]. However, molecular testing of phase I study participants from MD Anderson identified a PIK3CA mutation rate of 36% in squamous cervical cancer [29, 30]. At the Dana-Farber/Harvard Cancer Center (DFHCC), patients' tumors are frequently genotyped for oncogenic mutations and our preliminary data support this higher rate of PIK3CA mutation [31]. K-RAS and H-RAS mutations have also each been reported at 10% and 22% [9, 29, 32]. The co-mutation rates of PIK3CA and RAS are unknown but studies to explore this are ongoing at the DFHCC in archived samples.

To complete the translational research objectives listed above, primary tumor and blood will be collected from all women who consent to participate in the trial. Additionally patients with tumors that are accessible tumors for in-office biopsies (i.e. vaginal recurrences) will be given the *option* of undergoing pre-treatment and post-treatment biopsies. These tissues will be snap frozen tissue and amenable to phospho-protein analysis thereby allowing investigation of negative feedback loops within the RTK-RAS-ERK and PI3K pathways. The details of these procedures are noted in Appendix H.

3. PARTICIPANT SELECTION

3.1 Inclusion Criteria

Participants must meet the following criteria on screening examination to be eligible to participate in the study:

- **3.1.1** Participants must have histologically or cytologically confirmed cervical cancer which is now recurrent or metastatic and is refractory to curative therapy or established treatments. Histologic or cytologic confirmation of the original primary tumor is required. All histologic types of cervical origin are permitted.
- **3.1.2** All patients must have measurable disease as defined by RECIST 1.1. Measurable disease is defined as at least one lesion that can be accurately measured in at least one dimension (longest diameter to be recorded). Each lesion must be ≥ 10 mm when measured by spiral CT, MRI or caliper measurement by clinical exam; or ≥ 20 mm with conventional techniques. Lymph nodes must be ≥ 15 mm in short axis when measured by CT or MRI.
- **3.1.3** Prior Therapy:
 - Patients must have had one prior chemotherapeutic regimen for management of cervical carcinoma. Initial treatment may include chemotherapy, chemotherapy and radiation therapy, and/or chemotherapy as consolidation/maintenance therapy. Chemotherapy administered in conjunction with primary radiation as a radio-sensitizer will not be counted as a systemic chemotherapy regimen.
 - Patients are allowed to receive, but are not required to receive, one additional prior treatment regimen (including a single chemotherapeutic, a combination of chemotherapeutics, or biologic drugs such as bevacizumab) for management of their recurrent or persistent disease.
 - Patients must have NOT received any class of drugs targeted to the PI3K pathway (such has PI3K inhibitors or mTOR inhibitors) or RAS-ERK pathway for management of recurrent or persistent disease.
- **3.1.4** Age \geq 18 years. Because no dosing or adverse event data are currently available on the use of GSK1120212 and GSK2141795 in participants < 18 years of age, children are excluded from this study. Cervical cancer is very rare in the pediatric population.
- **3.1.5** Life expectancy of greater than 3 months.
- **3.1.6** ECOG performance status ≤ 2 (see Appendix A).
- **3.1.7** Participants must have normal organ and marrow function as defined below:
 - Absolute Neutrophil Count (ANC) \geq 1,500/mcL

- Platelets \geq 100,000/mcL
- Hemoglobin $\geq 9.0/dL$
- PT/INR and PTT $\leq 1.5 \times$ institutional ULN
- AST (SGOT) and ALT (SGPT) $\leq 2.5 \times$ institutional ULN
- Total bilirubin within normal institutional limits (isolated bilirubin > $1.5 \times$ institutional ULN is acceptable if bilirubin is fractionated and direct bilirubin <35%)
- Albumin $\geq 2.5 \text{ g/dL}$
- Creatinine \leq institutional ULN or creatinine clearance \geq 50 mL/min/1.73 m² for subjects with creatinine levels above institutional normal or \geq 50 mL/min 24-hour creatinine clearance
- Left ventricular ejection fraction (LVEF) ≥ institutional LLN by ECHO or MUGA
- Fasting Blood Glucose within institutional normal limits (see Exclusion Criterion 3.26)
- **3.1.8** Availability of a formalin fixed paraffin embedded (FFPE) block of cancer tissue from the original or most recent biopsy for mutational analysis. Availability must be confirmed prior to enrollment.
- **3.1.9** Blood pressure well controlled and must have systolic < 140 mmHg and diastolic < 90 mmHg.
- **3.1.10** The effects of GSK1120212 (trametinib) and GSK2141795 on the developing human fetus at the recommended therapeutic dose are unknown. For this reason, women of childbearing potential must agree to use two forms of contraception (hormonal or barrier method of birth control; abstinence) prior to study entry and for the duration of study participation. Should a patient become pregnant or suspect she is pregnant while she is participating in this study, she should inform the treating physician immediately.
- **3.1.11** Toxicities of prior therapy (excepting alopecia) should be resolved to \leq grade 1 per the revised NCI Common Terminology Criteria for Adverse Events (CTCAE) version 4.0. All appropriate treatment areas should have access to a copy of the CTCAE version 4.0.
- **3.1.12** GSK1120212 (trametinib) and GSK2141795 are oral medications. Patients must be able to tolerate oral medications and not have gastrointestinal illnesses that would preclude absorption of GSK1120212 and GSK2141795.
- **3.1.13** Ability to understand and willingness to sign a written informed consent document.

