5.5 Duration of Follow Up

Participants will be followed for 3 years after removal from study or until death, whichever occurs first. Participants removed from study for unacceptable adverse events will be followed until resolution or stabilization of the adverse event. Date and cause of death should be provided for participants who become deceased within the 3-year interval following removal from the study. Should a participant become pregnant while on trial, the patient will be withdrawn from the study. However, the outcome of the pregnancy and the newborn's health, if the pregnancy is carried to term, will be monitored.

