- c. If clinically indicated, assessments during subsequent cycles can occur more frequently.
- **d.** Final study visit should occur 21 days (±7 days) after last dose of study drug.
- e. Medical history and interim history for Cycle 1 Day 8 and Day 22 can be obtained through a phone call to the participant. Hematology and clinical chemistry can be obtained locally.
- f. Physical exams should be completed as follows:
 - Screening physical exam should include: the evaluation of the head, eyes, ears, nose, and throat, cardiovascular, dermatological, musculoskeletal, respiratory, gastrointestinal and neurological systems.
 - After screening, targeted physical examinations should be limited to systems of primary relevance and those systems associated with symptoms.
- **g.** If completed within 72 hours prior to dosing, this assessment does not need to be repeated.
- h. Hematology should include: red blood cell count, total white blood cell count, hemoglobin, hematocrit, platelet count, WBC differential (absolute)
- i. Clinical chemistry should include: sodium, BUN, creatinine, bicarbonate, chloride, calcium, LDH, phosphorus, GGT, magnesium, potassium, total protein, albumin, SGOT (AST), SGPT (ALT), alkaline phosphatase, total bilirubin
- j. Coagulation should include: prothrombin time (PT)/international normalized ratio (INR) and activated partial thromboplastin time (aPTT).
- k. Perform only in women of child-bearing potential. A serum pregnancy test should be performed at screening; subsequent pregnancy tests may be either
serum or urine.

- I. Should be collected pre-dose while the participant is on treatment. If 1,5-AG test is not available in a given country, the analyte is not required to be performed in that country.
- m. A single 12-lead ECG should be performed at screening, prior to dosing on Day 1 and Day 15 of Cycle 1, and prior to dosing on Day 1 of each subsequent cycle.
- **n.** Either an ECHO or MUGA should be performed to assess LVEF at screening, Cycle 2 Day 1, then every 12 weeks, at the final study visit, and as symptomatically warranted
- **o.** Ophthalmic exam will include indirect and direct fundoscopy, visual acuity (corrected), visual field examination, tonometry, and color fundus photos. Additional ophthalmic exams will be performed if symptomatically warranted.
- p. Refer to the Lab Manual and Section 8.7 of the protocol.

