11.4 Reporting to the Study Sponsor

11.4.1 Serious Adverse Event Reporting

All serious adverse events that occur after the initial dose of study treatment, during treatment, or within 30 days of the last dose of treatment must be reported to the DF/HCC Overall Principal Investigator on the local institutional SAE form. This includes events meeting the criteria outlined in Section 11.1.2, as well as the following:

- Grade 2 (moderate) and Grade 3 (severe) events that are unexpected and at least possibly related/associated with the intervention.
- All Grade 4 (life-threatening or disabling) events that are unexpected or not specifically listed in the protocol as not requiring reporting.
- All Grade 5 (fatal) events while the participant is enrolled and actively participating in the trial OR when the event occurs within 30 days of the last study intervention.

Note: If the participant is in long term follow up, report the death at the time of continuing review.

Participating investigators must report each serious adverse event to the DF/HCC Overall Principal Investigator within 1 business day of learning of the occurrence. In the event that the participating investigator does not become aware of the serious adverse event immediately (e.g., participant sought treatment elsewhere), the participating investigator is to report the event within 1 business day after learning of it and document the time of

his or her first awareness of the adverse event. Report serious adverse events by facsimile (preferred), email, or telephone to:

[name] [contact] **[contact]** [contact] Email: [contact]

Within the following 24-48 hours, the participating investigator must provide follow-up information on the serious adverse event. Follow-up information should describe whether the event has resolved or continues, if and how the event was treated, and whether the participant will continue or discontinue study participation.

For multi-institution studies where a DF/HCC investigator is serving as the Overall Principal Investigator, each participating institution must abide by the reporting requirements set by the DF/HCC. This applies to any medical event equivalent to an unexpected grade 2 or 3 with a possible, probable or definite attribution, unexpected grade 4 toxicities, and grade 5 (death) regardless of study phase or attribution.

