11.9 Monitoring of Adverse Events and Period of Observation

All adverse events, both serious and non-serious, and deaths that are encountered from initiation of study intervention, throughout the study, and within 30 days of the last study intervention should be followed to their resolution, or until the participating investigator assesses them as stable, or the participating investigator determines the event to be irreversible, or the participant is lost to follow-up. The presence and resolution of AEs and SAEs (with dates) should be documented on the appropriate case report form and recorded in the participant's medical record to facilitate source data verification.

For some SAEs, the study sponsor or designee may follow-up by telephone, fax, and/or monitoring visit to obtain additional case details deemed necessary to appropriately evaluate the SAE report (e.g., hospital discharge summary, consultant report, or autopsy report).

Participants should be instructed to report any serious post-study event(s) that might reasonably be related to participation in this study. Participating investigators should notify the DF/HCC Overall Principal Investigator and their respective IRB of any unanticipated death or adverse event occurring after a participant has discontinued or terminated study participation that may reasonably be related to the study.

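### Section 3.1.10 sets no contraception interval after the last dose; if study participation ends by the final visit, about 14% (day 14), 5% (day 21) or 2% (day 28) of trametinib may remain

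*Combined protocol and SAP*

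**What the plan says.** Section 3.1.10 is the only contraception rule in the text available. It states that the fetal effects of both drugs are unknown and requires two forms of contraception, "hormonal or barrier method of birth control; abstinence) prior to study entry and for the duration of study participation". It continues: "Should a patient become pregnant or suspect she is pregnant while she is participating in this study, she should inform the treating physician immediately". Section 3.2.9 excludes pregnant women because teratogenic or abortifacient effects are possible.

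No section defines study participation. The places that bear on when it ends are these:

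- Section 9, footnote d: "Final study visit should occur 21 days (±7 days) after last dose of study drug".
- Section 5.5: "Participants will be followed for 3 years after removal from study or until death, whichever occurs first".
- Section 5.5, on pregnancy: "Should a participant become pregnant while on trial, the patient will be withdrawn from the study". It then provides for monitoring the outcome of that pregnancy.
- Section 11.4.1 requires fatal events to be reported "while the participant is enrolled and actively participating in the trial OR when the event occurs within 30 days of the last study intervention".
- Section 11.9 says that adverse events arising up to and "within 30 days of the last study intervention should be followed to their resolution". It also asks investigators to notify unanticipated events occurring "after a participant has discontinued or terminated study participation that may reasonably be related to the study".

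Section 2.2.1 gives trametinib a mean effective half-life of about 5 days, with no range. Section 2.2.2 gives GSK2141795 a mean effective half-life of 3.0 days, ranging from about 1.3 to 5.5 days.

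**The concern.** The reason for contraception is possible fetal exposure, and that lasts as long as drug is present. The rule would therefore be expected to run from the last dose. Instead it is tied to an undefined term, so sites could apply it differently. A site that treats the final study visit as the end of participation could let contraception stop between day 14 and day 28 after the last dose, when some drug may still be in the body.

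The wording for pregnancy has the same limit. The duty to notify in 3.1.10 and the outcome monitoring in 5.5 both refer to a pregnancy that occurs on study, and neither names a conception shortly after the last dose. What is at stake is participant and fetal safety. The response-rate design and its analysis are not touched.

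**Working it through.** **Step 1: when participation ends.** Footnote d calls the visit at 21 ±7 days the final study visit. Section 5.5 starts the 3-year follow-up after removal from study, and 11.9 recognises a period after participation has ended. Together these make the final visit the most natural end point. Section 11.4.1 adds little, because describing someone as actively participating leaves room for a less active phase. Against this, 14.3 says participants are followed for up to 3 years, and 12.1.2 has a form for follow-up visits or calls. The end point is therefore an inference. The visit window runs from 21 − 7 = day 14 to 21 + 7 = day 28.

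**Step 2: drug remaining.** The documents give no residual-drug figure to reproduce. Assume single-exponential decline from the last dose, with t in days and h the effective half-life:

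fraction remaining = 0.5^(t/h)

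For trametinib with h = 5: 0.5^(14/5) = 0.1436, 0.5^(21/5) = 0.0544, 0.5^(28/5) = 0.0206.

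| Drug and half-life | Day 14 | Day 21 | Day 28 | Day 30 |
|---|---|---|---|---|
| Trametinib, 5 days (stated mean) | 14.4% | 5.4% | 2.1% | 1.6% |
| GSK2141795, 3.0 days (stated mean) | 3.9% | 0.8% | 0.2% | 0.1% |
| GSK2141795, 5.5 days (longest stated) | 17.1% | 7.1% | 2.9% | 2.3% |
| Trametinib, 4 days (assumed) | 8.8% | 2.6% | 0.8% | 0.6% |
| Trametinib, 7 days (assumed) | 25.0% | 12.5% | 6.3% | 5.1% |

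The last two rows are a sensitivity range of my choosing, since the protocol gives only the trametinib mean.

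**Step 3: a benchmark.** Section 3.2.2 uses five half-lives, among other limits, for washout of other investigational agents before entry. It is not a contraception standard in this protocol, but it gives a scale. Five half-lives is 5 × 5 = 25 days for mean trametinib, 5 × 3.0 = 15 days for mean GSK2141795 and 5 × 5.5 = 27.5 days for its longest value. The longest half-life for which five half-lives have passed is 14/5 = 2.8 days at day 14, 21/5 = 4.2 at day 21, 28/5 = 5.6 at day 28 and 30/5 = 6.0 at day 30. The nominal visit thus falls 25 − 21 = 4 days short for mean trametinib, and the late edge of the window does not fall short.

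**Step 4: what is already covered.** The calendar has a pregnancy test at the off-treatment visit. Section 11.5 requires pregnancy exposure to be reported, outcomes included, with no time limit. Section 11.1.2 counts a congenital anomaly as a serious adverse event. Section 11.9 asks participants to report related serious events after the study. These detect and report; none of them extends contraception.

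**The case against.** The strongest objection is that participants usually learn how long to use contraception from the consent form, which is not part of the review copy. The Investigator's Brochures, to which Section 2.2 refers, were not available either. Either may state an interval. A reader might infer from 3.1.10 that participants are left unprotected after treatment; the documents do not support that. They show a gap in one eligibility criterion.

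A second objection is that the early end point is inferred. If participation includes the 3-year follow-up, the gap disappears. This stands as a limit on the claim, although that reading would mean two contraceptive methods for three years after treatment, which 3.1.10 gives no sign of intending. In the other direction, a reader might infer from the schema, which takes participants with progression off the trial, that contraception could end sooner than day 14. The calendar still schedules a study visit after the last dose, so I do not rely on that reading.

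Third, the percentages have no stated safety meaning. The protocol gives no fetal exposure threshold, and the less worrying figures belong beside the others: 2.1% of trametinib at day 28, and 0.8% of GSK2141795 at day 21 at its mean half-life. This stands too.

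Fourth, 30 days is borrowed from the reporting windows in 11.4.1 and 11.9. At an assumed trametinib half-life of 7 days, 5.1% would remain at day 30, close to the 5.4% found at day 21 for the mean. Thirty days should therefore be a minimum.

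**Conclusion.** The point holds as a minor precautionary safety gap. Section 3.1.10 uses an undefined term and sets no interval after the last dose. Under its most natural reading, contraception could stop with roughly 2% to 14% of trametinib remaining, and about 5% at the nominal visit. For GSK2141795, 0.8% to 7.1% would remain at the nominal visit, from the mean to the longest half-life.

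These figures rest on three assumptions: participation ends at the final visit, decline is single-exponential, and the effective half-lives apply after the last dose. Individuals will vary around the trametinib mean.

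A reader might go further and infer that the plan exposes a fetus to a harmful dose. The documents do not support that: they say fetal effects are unknown and give no level to compare with. Nor do they say how many of the 35 planned participants will be of childbearing potential. Pregnancy reporting is largely in place. What remains is the wording in 3.1.10 and 5.5.

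**What to change.** In 3.1.10, require contraception during treatment and for at least 30 days after the last dose of either drug, or longer if the Investigator's Brochures specify a longer interval. Thirty days matches the windows already in 11.4.1 and 11.9, and it covers five half-lives for any half-life up to 6.0 days. That includes the trametinib mean and the longest reported GSK2141795 value.

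Extend the notification sentence in 3.1.10 and the outcome follow-up in 5.5 to conceptions within the same interval. Align the consent form.

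The cost is a few sentences and a check of the consent form, with no added procedure. Compared with the final-visit reading, women of childbearing potential would use contraception for 30 − 28 = 2 to 30 − 14 = 16 more days, or 30 − 21 = 9 more days from the nominal visit.
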